1.1 Study Background and Rationale

Exercise is at the cornerstone of type 1 diabetes (T1D) management (1). However, blood glucose stability during exercise, and for up to 12-24 hours in recovery, remains a major challenge (2). A fear of hypoglycemia deters many patients from engaging in aerobic exercise (3). For those who choose to exercise on a regular basis, hypoglycemia is a common complaint that often requires breaks in sports and competition, games and training (1). To reduce the incidence of hypoglycemia during and immediately after exercise, patients are recommended to reduce their bolus dose at the meal preceding exercise by 25-75% (1), however, this approach frequently results in pre-exercise hyperglycemia, particularly if the exercise is performed 2 hours or more after the meal (2,4,5). Even exercise in the fasting state in patients on continuous subcutaneous insulin infusion (CSII) promotes a drop in glycemia if basal insulin levels are unadjusted (6).

Post-exercise nocturnal hypoglycemia is also very common in T1D, with roughly 50% of young patients developing the condition about 7-11 hours after the end of vigorous afternoon exercise (7). If insulin administration occurs to correct post-exercise meal-related hyperglycemia (often called rebound hyperglycemia), severe post-exercise hypoglycemia can occur which may even result in death (8). Patients can reduce the dose of rapid-acting insulin administered with the dinner meal after late day exercise to reduce nocturnal hypoglycemia risk (9) or lower basal insulin delivery for 6 hours at bedtime (10) to help mitigate risk, but these strategies often result in hyperglycemia (9, 10). Although extra carbohydrate ingestion not covered by insulin administration can help prevent hypoglycemia during and after exercise (11), excessive intake defeats the ability of the patient to have a negative caloric balance, thereby limiting the capacity for patients to maintain or lose body weight.

Patients on insulin pump therapy have the flexibility to reduce basal insulin delivery in anticipation of exercise and in recovery to help guard against hypoglycemia. The International Society for Pediatric and Adolescent Diabetes guidelines recommend that basal insulin reductions should be done 60-90 minutes before the start of exercise so that circulating insulin levels are lowered by the start of the activity (12). This is a somewhat cumbersome and unpredictable task that is usually not performed correctly, even by the most educated and motivated patients. Since glucose production by the liver during moderate intensity exercise is primarily facilitated by a rise in the glucagon to insulin ratio (13) and patients with T1D have a reduction in this ratio during exercise because of a relative peripheral hyperinsulinemia (13) and impaired glucagon secretion (14), it may be better to attempt to change this ratio by the administration of glucagon at the onset of exercise. The recent development of a more stable form of soluble glucagon (e.g. G-Pen Mini™ glucagon from Xeris Pharmaceuticals, Inc. (Xeris)) has given researchers and clinicians the possibility of using this product as a preventative strategy to combat exercise-associated hypoglycemia. However, to date, studies have not been done that examine the efficacy of mini-dose glucagon administration for exercise.

103 **1.2 Synopsis of Study Protocol**

104 This project focuses on the development of a new strategy for the prevention of exercise-
105 associated hypoglycemia using mini-dose glucagon.

106

107 **1.2.1 Objectives**

108 The primary objective of the protocol is to determine if the administration of mini-dose glucagon
109 administered subcutaneously just before exercise produces better glucose stability than no
110 adjustments for moderate intensity exercise in patients with T1D. It will also be assessed
111 whether mini-dose glucagon before exercise produces better glucose stability than basal insulin
112 reductions or extra carbohydrate consumption. In addition, the impact of mini-dose glucagon
113 administration before exercise on nocturnal glycemia after exercise will be evaluated.

114

115 **1.2.2 Study Design**

116 This is a randomized, 4-way crossover trial.

117

118 **1.2.3 Major eligibility criteria**

- 119 • Clinical diagnosis of presumed autoimmune type 1 diabetes, receiving daily insulin
- 120 • Age 18-<65 years
- 121 • Duration of type 1 diabetes ≥ 2 years
- 122 • Random C-peptide < 0.6 ng/ml
- 123 • Using CSII (e.g., insulin pump) for at least 6 months
- 124 • Exercises regularly: i.e. ≥ 30 minutes moderate or more vigorous aerobic activity ≥ 3
125 times/week

126

127 See section 2.2 for a complete listing of inclusion and exclusion criteria.

128

129 **1.2.4 Visit Schedule**

130 1. Screening/Baseline Visit

- 131 ○ Sign informed consent form and assessment of eligibility
- 132 ○ Assessment of VO_2 max for fitness evaluation and for the determination of
133 exercise intensity for the experimental trials.

134

135 2. Randomized Crossover Trial

136 Each participant will undergo four aerobic exercise sessions (in random order) in the
137 CRC, with different strategies for glucose regulation:

- 138 • Control Trial: Fasted exercise, no basal insulin reduction
- 139 • Strategy 1: Fasted exercise, basal insulin reduction only (50% reduction in basal rate
140 five minutes before exercise, for the duration of the exercise)
- 141 • Strategy 2: Fasted exercise, no basal adjustment + pre-exercise glucose tabs (buccal
142 route-40 grams in total)
- 143 • Strategy 3: Fasted exercise, no basal adjustment + pre-exercise mini-dose glucagon
144 (sc)

145

146 In all 4 sessions, aerobic exercise will be performed in the fasted state (before a
147 standardized meal) for 45 minutes at ~50-55% of the participant's pre-determined aerobic

148 capacity (see flow chart in section 1.4). The strategies for select sessions will be blinded as
149 described in section 3.2.2.

150

151 **1.2.5 Primary Outcome**

152 The primary outcome for this study will be the glycemic response during exercise and
153 early recovery.

154

155 **1.2.6 Main Safety Outcomes**

- 156 • Hypoglycemic events
- 157 • Hyperglycemic events
- 158 • Dizziness, pallor and other symptoms of poor perfusion and/or exercise
159 intolerance

160

161 **1.3 General Considerations**

162 The study is being conducted in compliance with the policies described in the study policies
163 document, with the ethical principles that have their origin in the Declaration of Helsinki, with
164 the protocol described herein, and with the standards of Good Clinical Practice.

165

166 A risk-based monitoring approach will be followed, consistent with the FDA “Guidance for
167 Industry Oversight of Clinical Investigations — A Risk-Based Approach to Monitoring” (August
168 2013).

[figure not shown]
169

170 The mini-dose glucagon preparation (G-Pen Mini™) is not FDA approved. Therefore, an IND
171 (#119733) has been received from the FDA by Xeris in order to conduct the study. The Daily
172 Dose™ syringes used to inject the mini-dose glucagon are also not FDA approved in the U.S.
173 While use of the syringes will be considered investigational, the study investigators believe they
174 do not meet significant risk device criteria per 21 CFR 812.3(m) and thus an IDE from the FDA
175 is not needed.

176

177
178
179
180
181

1.4 Flow Chart of Exercise Sessions

182
183
184
185

186 **CHAPTER 2: PARTICIPANT ELIGIBILITY AND ENROLLMENT**

187
188 **2.1 Study Population**

189 The crossover trial will include 16 participants who complete the study. Participants may be
190 replaced if a participant does not complete the entire protocol. Each site is expected to have 8
191 participants completing the crossover trial, but this could be increased at a given site if necessary
192 to meet the recruitment goal.

193
194 **2.2 Eligibility**

195 To be eligible for the study, a participant must meet the following inclusion criteria and none of
196 the exclusion criteria:

197
198 **2.2.1 Inclusion Criteria**

- 199 1) Clinical diagnosis of presumed autoimmune type 1 diabetes, receiving daily insulin
200 2) Age 18-<65 years
201 3) Duration of T1D ≥ 2 years
202 4) Random C-peptide < 0.6 ng/ml
203 5) Using CSII (e.g., insulin pump) for at least 6 months, with no plans to discontinue pump
204 use during the study
205 6) Exercises regularly, i.e. ≥ 30 minutes moderate or more vigorous aerobic activity $\times \geq 3$
206 times/week
207 7) Body mass index (BMI) < 30 kg/m²
208 8) Females must meet one of the following criteria:
209 a. Of childbearing potential and not currently pregnant or lactating, and agrees to
210 use an accepted contraceptive regimen as described in the study procedure manual
211 throughout the entire duration of the study; or
212 b. Of non-childbearing potential, defined as a female who has had a hysterectomy or
213 tubal ligation, is clinically considered infertile or is in a menopausal state (at least
214 1 year without menses)
215 9) In good general health with no conditions that could influence the outcome of the trial,
216 and in the judgment of the investigator is a good candidate for the study based on review
217 of available medical history, physical examination and clinical laboratory evaluations
218 10) Willing to adhere to the protocol requirements for the duration of the study
219 11) Must be enrolled in the T1D Exchange clinic registry or willing to join the registry

220
221
222 **2.2.2 Exclusion Criteria**

- 223 1) One or more severe hypoglycemic episodes in the past 12 months (as defined by an
224 episode that required third party assistance for treatment)
225 2) Active diabetic retinopathy (PDR or VH in past 6 months) that could potentially be
226 worsened by exercise protocol
227 3) Peripheral neuropathy with insensate feet
228 4) Cardiovascular autonomic neuropathy with inappropriate heart rate response to exercise
229 (could be diagnosed with screening EKG: rule out tachycardia with fixed RR interval)
230 5) Use of non-insulin anti-diabetic medications
231 6) Use of beta-blockers

- 232 7) Use of agents that affect hepatic glucose production such as beta adrenergic agonists,
233 xanthine derivatives
234 8) Use of Pramlintide
235 9) Currently following a very low calorie or other weight-loss diet
236 10) Participation in other studies involving administration of an investigational drug or
237 device within 30 days or 5 half-lives, whichever is longer, before screening for the
238 current study or planning to participate in another such study during participation in the
239 current study
240

241 **2.3 Screening Visit and Patient Enrollment**

242 Potential participants will have a screening visit to assess eligibility through the elicitation of a
243 medical history and performance of a physical examination by a study investigator. Screening labs
244 will be collected as outlined in section 2.3.1. A urine pregnancy test will be done for females with
245 child-bearing potential. Clinical sites will keep a record of the reason why screened participants
246 are not enrolled.
247

248 **2.3.1 Laboratory Testing**

249 The following laboratory testing results, typically obtained as part of routine care, will be
250 assessed by the investigator as part of the general assessment for eligibility. Time periods prior to
251 enrollment for which each test should have been performed are given in parenthesis.

- 252 • Basic Metabolic Panel (within 3 months)
 - 253 • Complete Blood Count (within 3 months)
 - 254 • Liver Function Panel (within 6 months)
 - 255 • Random C-peptide (since diagnosis, subjects must be < 0.6 ng/ml)
 - 256 • Lipids (within 6 months)
 - 257 • Thyroid-Stimulating Hormone (within 12 months)
 - 258 • HbA1c will be measured using point-of-care device or local lab if not available within the
259 3 months prior to enrollment.
 - 260 • Urine pregnancy test if indicated (see inclusion criteria)
- 261

262 **2.3.2 Historical Information and Physical Exam**

263 A history will be elicited from the participant and extracted from available medical records with
264 regard to the participant's diabetes history, current diabetes management, other past and current
265 medical problems, past and current medications, drug allergies, and family history. A standard
266 physical exam (including vital signs and height and weight measurements) will be performed by
267 the study investigator or his or her designee (an endocrinologist, endocrine fellow, endocrine
268 nurse practitioner or a physician assistant).
269

270 **2.3.3 Informed Consent**

271 The study will be discussed with potential participants. A copy of the consent form will be
272 provided to the participant and another copy will be added to the participant's clinic chart.
273

274 Written informed consent will be obtained prior to performing any study-specific procedures that
275 are not part of the participant's routine care.
276

277 **2.3.3.1 Authorization Procedures**

278 As part of the informed consent process, each participant will be asked to sign an authorization
279 for release of personal information. The investigator, or his or her designee, will review what
280 study specific information will be collected and to whom that information will be disclosed.
281 After speaking with the participant, questions will be answered about the details regarding
282 authorization.
283

284 **2.3.4 T1D Exchange Clinic Registry**

285 If a participant is not already enrolled in the T1D Exchange clinic registry, he/she will become
286 part of the registry when joining this study. Registry participants' information from their
287 medical record may be entered into the registry database at least once a year and they will have
288 an opportunity to provide their email address to be contacted in the future about other studies for
289 which they may be eligible. Participants also may be asked to complete a questionnaire(s) either
290 on a computer, paper, or via telephone. Participants may be given the option to have
291 questionnaires emailed to them and may decide whether or not to complete a questionnaire each
292 time they are asked.
293

CHAPTER 3: STUDY PROTOCOL

3.1 Procedures Prior to First Exercise Session

- Assessment of VO₂max following the Bruce protocol
- Optimization of basal insulin dose as per investigator's usual routine

3.2 Exercise Sessions

Each participant will be assigned to a sequence of control trial, strategy 1, strategy 2, and strategy 3 through a randomization process as outlined in section 3.2.2. Each exercise session will be separated by at least 3 days and participants will be expected to complete all sessions within 12 weeks from the time of the baseline/screening visit. Participants will be advised to avoid any vigorous exercise within 24 hours before or after the laboratory-based exercise tests. Subjects will be asked about activity to monitor adherence to these recommendations.

3.2.1 Prior to Exercise Sessions

The day before each exercise session participants will:

- Insert new insulin infusion set into abdomen or upper buttock (ensure not in exercising limb).
- For CGM users, insert a new CGM sensor
- For non-CGM users, come into clinic to have a CGM sensor inserted to use with a blinded receiver

The participant will be contacted by the research staff on the evening before and the morning of each exercise session to review glucose levels and help mitigate pre-exercise hyperglycemia or hypoglycemia.

- If at the time of the morning call, the glucose concentration is below target (<100 mg/dL), then supplemental fast-acting carbohydrate will be taken. If above target (>140 mg/dL), then a conservative correction bolus will be recommended (based on insulin sensitivity factor).

The participant will arrive at the CRC in a fasted state (minimum of 8 hour fast) by 9 a.m., but exercise sessions can begin as early as 8 a.m.

- Blood glucose concentration will be checked upon arrival to the clinic. Oral glucose or IV glucose may be given to bring participant into range before exercise.
- Females will have a urine pregnancy test performed prior to each exercise session (if applicable).

Before an exercise session can begin:

1. Participant glucose must be: 100- 140 mg/dL (venous, plasma)
2. Last insulin bolus (mealtime or correction) should be ≥ 3 hours previously

3.2.2 During Exercise Sessions

At each visit, participants will complete one of the following four exercise sessions (sequence of sessions determined by randomization):

339 Control Trial: No basal insulin adjustment, no carbohydrate intake until glucose drops <70
340 mg/dL. Then 20 grams of dextrose will be given orally.
341 Strategy 1: Basal insulin reduction to 50% five minutes before the start of exercise. Basal
342 insulin rate will be returned to usual rate 45 minutes after the start of exercise.
343 Strategy 2: Dextrose tabs taken orally (20 grams) five minutes before the start of exercise and
344 at 30 minutes of exercise (total 40 grams).
345 Strategy 3*: Glucagon (150 µg) five minutes before the start of exercise (SQ-abdomen).

346
347 *The dose for strategy 3 will likely be 150 µg, but may be modified to be lower or higher, with a
348 possible range of 75-300 µg. One or more pilot phases of up to 6 participants will be conducted
349 prior to study initiation to determine the most appropriate dose.

350
351 The participant's pump will be blinded during the control trial, strategy 1, and strategy 3 and an
352 injection of saline will be given during the control trial and strategy 1 so that participant is
353 blinded to strategy.

354
355 Exercise will consist of moderate intensity aerobic activity (treadmill jogging/brisk walking)
356 performed at 50-55% of predetermined VO₂max for 45 minutes. Continuous heart rate
357 measurements will be conducted along with intermittent ratings of perceived exertion (Borg 6-20
358 scale).

359
360 Exercise will be terminated if:
361 • Glucose is <70 mg/dL; participants will be treated for hypoglycemia (initially 20 grams
362 of oral dextrose tabs or IV dextrose or IM glucagon depending on the severity of the
363 hypoglycemia).
364 • Participants experience dizziness, pallor and other symptoms of poor perfusion and or
365 exercise intolerance

366
367 Any treatment given will be recorded.

368
369 Participants who are not able to complete an exercise session due to termination will still
370 complete remaining study procedures as outlined in sections 3.2.3 and 3.2.4.

371 372 **3.2.3 Following Exercise Sessions**

373 Following each exercise session, the participant will rest for 30 minutes and then consume a
374 standardized meal containing 44-50 grams of carbohydrate that constitute ~55% of calories,
375 together with ~20% calories from protein and ~25% calories from fat. The amount of bolus
376 insulin given will be based on the carbohydrate content of the meal and the patient's own
377 individualized insulin to carbohydrate ratio. Insulin will be administered five minutes before the
378 standardized meal. In the first phase of the experiments, insulin "corrections" will not be given
379 unless subjects have post exercise/ pre meal hyperglycemia ≥270 mg/dl. If hypoglycemia occurs
380 prior to the meal, subjects will be treated with 20 grams of fast acting carbohydrate prior to meal
381 consumption.

382
383 The participant will be monitored for at least 2 hours after the meal prior to discharge.

384

385 Participants will be given a meal log and another standardized meal to take with them at
386 discharge. Participants will be instructed to eat the standardized meal for their next meal and log
387 the time it was eaten. They will also be asked to log any meals they consume through noon the
388 following day.

389
390 For participants using the blinded CGM, the sensor will be removed at 12PM the next day at
391 home (~ 24 hours after the end of exercise). The participant will bring the device to the next
392 visit or mail it back to the clinic.

393
394 Participants will receive a phone call the day after each exercise session to elicit any adverse
395 events.

396
397 For CGM users, the CGM data will be downloaded at each visit and arrangements made to
398 transmit the data following the last exercise session.

399
400 The participant's insulin pump will be downloaded at each visit and arrangements made to
401 transmit the data following the last exercise session.

402

403 **3.2.4 Sample collection**

404 Blood samples collected through a venous catheter with plasma glucose measured by an YSI
405 analyzer. Blood samples will be collected at:

- 406 • Baseline (at -30, -15, -5, 0 min)
- 407 • During exercise (at 5, 10, 15, 25, 35, 45 min)
- 408 • In recovery post exercise (at 50, 55, 60, 75 min)
- 409 • Regularly following a standardized mixed meal for 90 minutes (at 90, 105, 120, 135, and
410 165 min)

411

412 Plasma from the collected blood samples will be used to measure the following hormones,
413 proinflammatory markers and metabolites at baseline, during exercise, in recovery post exercise,
414 and regularly following the standardized mixed meal:

- 415 • Insulin
- 416 • Glucagon
- 417 • Cortisol
- 418 • Growth hormone
- 419 • Catecholamines (epinephrine and norepinephrine)
- 420 • Interleukin-6, tumor necrosis factor- α
- 421 • Nonesterified fatty acids
- 422 • β -hydroxybutyrate
- 423 • Lactate

424

CHAPTER 4: ADVERSE EVENT REPORTING AND SAFETY MONITORING

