6.1 Sample Size

A target of 16 subjects, with replacement of any participants who do not complete the study, was selected as a reasonable sample size for this feasibility study. Considering the primary outcome of glucose, power was approximated using a t-test. The table below provides power estimates based on a paired t-test comparing glucose during the mini-dose glucagon treatment and glucose during the control treatment.

Power Estimates*

Mean difference (mg/dL)	Correlation						
	0.2	0.3	0.4	0.5	0.6	0.7	0.8
20	32%	35%	40%	47%	55%	68%	84%
25	46%	51%	57%	65%	74%	85%	96%
30	60%	66%	73%	80%	88%	95%	99%
35	74%	79%	85%	91%	96%	99%	>99%

*Power was calculated for a sample size of 16 participants with a two-sided alpha of 0.05 and assuming a standard deviation of 40 mg/dL for each treatment. (A previous DirectNet exercise study was considered when estimating standard deviation [16].)

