38 based on a paired t-test comparing glucose during the mini-dose glucagon treatment and glucose
39 during the control treatment.

40
41 **Power Estimates***

Mean difference (mg/dL)	Correlation						
	0.2	0.3	0.4	0.5	0.6	0.7	0.8
20	32%	35%	40%	47%	55%	68%	84%
25	46%	51%	57%	65%	74%	85%	96%
30	60%	66%	73%	80%	88%	95%	99%
35	74%	79%	85%	91%	96%	99%	>99%

42 *Power was calculated for a sample size of 16 participants with a two-sided alpha of 0.05 and assuming a standard
43 deviation of 40 mg/dL for each treatment. (A previous DirectNet exercise study was considered when estimating
44 standard deviation [Tsalikian 2006].

45

46 **3.0 Analysis Plan**

47

48 **3.1 Sample collection**

49 Blood samples collected through a venous catheter with plasma glucose measured by an YSI
50 analyzer. Blood samples will be collected at:

- 51 • Baseline (at -30, -15, -5, 0 min)
- 52 • During exercise (at 5, 10, 15, 25, 35, 45 min)
- 53 • In recovery post exercise (at 50, 55, 60, 75 min)
- 54 • Regularly following a standardized mixed meal for 90 minutes (at 90, 105, 120, 135, and
55 165 min)

56

57 **3.2 Definitions of Time Periods**

- 58 • Exercise—45 minutes of scheduled exercise, even if participant terminated exercise early
- 59 • Early recovery—all time points through 30 minutes post exercise session
- 60 • Late recovery—all CGM data through noon the day after each exercise session will be
61 included. Periods of interest during late recovery include the below. Timing of meals
62 indicated on participant log; if log is missing or incomplete, meal timing will be
63 estimated.
 - 64 ○ Standard meal during study (30 minutes post exercise) to standard box lunch
65 provided at discharge
 - 66 ○ Box lunch provided at discharge to dinner (of participant's choice)
 - 67 ○ Dinner to 10:00 PM
 - 68 ○ 10:00 PM to 8:00 AM the day following exercise
 - 69 ○ 8:00 AM to noon the day following exercise

70

71 **3.3 Primary Outcome**

72 The primary outcome for this study will be glucose, as measured by YSI analysis, during
73 exercise and early recovery.

74

75 **3.3.1 Primary Analysis**

76 The primary analysis for this study will be a descriptive comparison of glycemic response during
77 exercise and early recovery between the mini-dose glucagon group (strategy 3) and the control
78 group. Summary statistics will be calculated. In the event that exercise is terminated early due to

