79 glucose <70 mg/dL and the participant is treated for hypoglycemia (or if participant is treated for
80 hypoglycemia during early recovery [prior to the meal]), the nadir glucose value will be carried
81 forward through the end of early recovery.

82

83 Analysis will follow the intent-to-treat principle with each visit allocated to one of the above
84 strategies (Section 1.0) according to the randomization assignment. Analysis will include
85 subjects who completed both the mini-dose glucagon and the control exercise session visits with
86 baseline glucose and at least three YSI glucose measurements during exercise and at least two
87 YSI glucose measurements during early recovery available from each visit.

88

89 To obtain a test of significance, a treatment comparison of glucose during exercise and early
90 recovery will be completed using a linear mixed model with repeated measures that accounts for
91 the correlation due to the cross-over design and the correlation due to multiple measures,
92 adjusting for baseline glucose level and any period effect. Regression diagnostics will be
93 performed and if the distribution of residuals is skewed, non-parametric methods and
94 transformations will be considered.

95

96 **3.4 Secondary Outcomes**

97 The following outcome measures will also be analyzed.

- 98 • Occurrence of hypoglycemia (<70 mg/dL) as measured by YSI analysis during exercise
99 or early recovery, at the visit level
- 100 • Occurrence of hyperglycemia (≥ 250 mg/dL) as measured by YSI analysis in the
101 following time periods: during exercise, after exercise in early recovery/prior to meal
102 ingestion and for 90 minutes after the meal (2 total hours after the end of exercise), at the
103 visit level
- 104 • Glucose levels after a standardized meal (glucose area under the curve analysis)
- 105 • Glucose levels in late recovery (afternoon and overnight following the exercise protocols-
106 CGM analysis)
 - 107 ○ Mean
 - 108 ○ Nadir
 - 109 ○ Area above and below curve threshold (i.e. area above or below 70-180 mg/dL)
 - 110 ○ % of time in range (70-180 mg/dL)
 - 111 ○ % of time below 70 mg/dL
 - 112 ○ Occurrence of hypoglycemia (<70 mg/dL) overnight

113

114 For sensor data after an exercise session to be included in the analysis, a subject must have at
115 least 12 hours (i.e., 144 CGM readings) from the window after the exercise session through noon
116 the following day.

117

118 **3.4.1 Secondary Analyses**

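### The nadir rule in SAP 3.3.1 misses sessions stopped for symptoms and then given glucose-raising rescue before scheduled minute 45, so post-rescue glucose enters the primary outcome

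*Protocol*

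**What the plan says.** Protocol 3.2.2 gives two separate grounds for ending exercise. One is glucose below 70 mg/dL, followed by treatment. The other applies if "Participants experience dizziness, pallor and other symptoms of poor perfusion and or" exercise intolerance, with no glucose condition attached. After either stop the remaining procedures continue, including blood sampling. Any treatment given is recorded.

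Protocol 6.2.2 and SAP 3.3.1 carry the nadir forward to the end of early recovery in some treated sessions. The SAP's trigger is exercise ended early for "glucose <70 mg/dL and the participant is treated for hypoglycemia (or if participant is treated for" hypoglycemia in early recovery, before the meal). Symptom stops are not named.

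SAP 3.2 defines the exercise period as "45 minutes of scheduled exercise, even if participant terminated exercise early". Early recovery runs through 30 minutes after the session. The primary window has ten samples: 5, 10, 15, 25, 35 and 45 min in exercise, and 50, 55, 60 and 75 min in early recovery.

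Protocol 3.2.3 also calls for 20 g of fast-acting carbohydrate if hypoglycemia occurs before the meal. Neither document plans an analysis by reason for stopping.

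**The concern.** The nadir rule keeps the effect of rescue carbohydrate from being counted as the effect of the assigned strategy. Its two triggers are a recorded stop reason with treatment, and a time period with treatment. Rescue itself is not the trigger. That leaves a gap between a symptom stop and scheduled minute 45. Rescue given there did not follow a stop caused by low glucose, and by SAP 3.2 it falls in exercise, not early recovery.

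The affected values go straight into the primary glucagon-control comparison. In a control session they raise the control mean and narrow the difference. In a glucagon session they widen it. With 16 participants, each session has a weight of one sixteenth in its strategy mean.

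**Working it through.** **The plan's own figure.** Protocol 6.1 and SAP 2.0 use a paired t-test with n = 16, SD 40 mg/dL per treatment and two-sided alpha 0.05. At correlation 0.5:

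- SD of the difference = 40 × √(2 × (1 − 0.5)) = 40 mg/dL
- SE = 40/√16 = 10 mg/dL
- At a mean difference of 30 mg/dL, noncentrality = 30/10 = 3 on 15 df, which gives power of 80.1%

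The table prints 80%, and all 28 cells agree to within one point. The power table is not in question; it supplies the SE used as a yardstick below.

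**The triggers applied to three sessions.**

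| Session | Stopped for glucose <70 and treated? | Treated in early recovery? | Values used after rescue |
|---|---|---|---|
| Stopped at 69 mg/dL, treated | Yes | – | Nadir |
| Stopped for symptoms at ≥70, treated at 55 min | No | Yes | Nadir |
| Stopped for symptoms at 25 min with 75 mg/dL, 68 at 35 min, treated then | No | No, 35 min is still exercise | Measured, post-rescue |

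The third session needs no departure from the protocol. The stop falls under the symptom criterion in Protocol 3.2.2, and the treatment follows Protocol 3.2.3.

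**Size for the third session.** The documents give no post-rescue glucose course. I assume a rise of R = 30 to 60 mg/dL, linear over 20 minutes from 35 min and then flat. Under the nadir rule the later samples would stay at 68. The fraction of R reached at each later sample is:

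- 45 min: 10/20 = 0.50
- 50 min: 15/20 = 0.75
- 55, 60 and 75 min: 1.00 each

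The sum is 0.50 + 0.75 + 3 × 1.00 = 4.25. The excess in the ten-sample mean is 4.25 × R/10:

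- R = 30: 12.75 mg/dL
- R = 60: 25.5 mg/dL

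One such session in one arm moves the unadjusted 16-participant difference by 12.75/16 = 0.80 to 25.5/16 = 1.59 mg/dL. That is 0.08 to 0.16 of the SE. Two such sessions in the same arm move it by 1.6 to 3.2 mg/dL.

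**Against the power table.** With a true difference of 30 mg/dL, correlation 0.5 and the SD held fixed, power becomes:

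| Shift in difference (mg/dL) | Power if narrowed | Power if widened |
|---|---|---|
| 0 | 80.1% | 80.1% |
| 0.75 | 78.0% | 81.9% |
| 1.5 | 75.9% | 83.7% |
| 3 | 71.4% | 86.9% |

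**The case against.** The main objection is that post-stop data are kept on purpose. SAP 3.2 says so, and SAP 3.3.1 analyzes by intent to treat at visit level. An untreated symptom stop has no rescue to contaminate later glucose, so measuring one session and holding another at its nadir is a contrast of untreated with treated. All of this stands, and it limits the point to rescued sessions.

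A reader might go further and infer that resting glucose after any symptom stop biases the trial toward glucagon. The documents do not support that:

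- **Side effects.** Protocol 4.2.1 reports no nausea or vomiting at 75-150 µg, and nausea in 4 of 12 subjects at 300 µg. The likely dose is 150 µg, and nausea is not among the named stopping symptoms.
- **Size.** Letting glucose fall unchecked to 45 min ignores the stop below 70 mg/dL and the nadir hold that follows. Take an untreated stop at 15 min with 75 mg/dL, flat afterward. Had exercise continued at an assumed fall of 0.5, 1.0 or 1.5 mg/dL per minute, the first sampled value below 70 would be 65 (35 min), 65 (25 min) or 60 (25 min), then held. The session mean differs by (5 + 6 × 10)/10 = 6.5, 7 × 10/10 = 7.0 or 7 × 15/10 = 10.5 mg/dL.
- **Direction.** It is not fixed, and similar stops in both arms would largely cancel.

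Dextrose for symptoms at 70 mg/dL or above in the control session would also go against Protocol 3.2.2, so the point does not rest on it.

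Another reading starts early recovery at the actual stop, which would bring the third session under the rule. That sits badly with the SAP's scheduled-time definition of exercise. If it is intended, it should be written down.

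Finally, this is a 16-person feasibility study with a descriptive primary analysis, and poor-perfusion events are tabulated as adverse events by strategy. That lowers the stakes but does not close the gap.

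**Conclusion.** The gap is real and narrow. Read literally, SAP 3.2 and 3.3.1 leave post-rescue glucose in the primary outcome when a session stops for symptoms at 70 mg/dL or above and is rescued before scheduled minute 45. The size is about 13-26 mg/dL in that session's mean and 0.8-1.6 mg/dL in the treatment difference per session, against an SE of about 10.

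These figures rest on the assumed 30-60 mg/dL rise over 20 minutes, treatment at 35 min, correlation 0.5 and simple means; the adjusted mixed model would differ somewhat. The documents do not say how often such sessions would occur. One is minor; several in one arm would matter. Nothing here shows that the plan favors glucagon, or that untreated symptom stops are mishandled.

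**What to change.** **Main change, SAP 3.3.1.** Apply the nadir carry-forward whenever glucose-raising rescue is given at any time from 0 min to the meal, whatever reason is recorded for stopping. State that the scheduled strategy 2 dextrose is not rescue. Starting at 0 min also leaves out glucose given beforehand to bring a participant into the starting range. This is an analysis rule only and changes no clinical procedure. Treatment is already recorded, and the SAP's version history says no analyses had been performed, so the rule could still be set in advance.

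**Optional additions.**

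- Pre-specify one sensitivity run of the mixed model with samples after an untreated symptom stop set to missing. Measured values stay in the main analysis.
- For that run, waive the requirement of at least two early-recovery values per visit. A stop at 15 or 25 min leaves none, so the participant's pair would otherwise be lost.
- Report early stops by reason, and minutes exercised, by strategy.

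**Cost.** One sentence, plus one model run and a short table if the additions are adopted. The additions need the stop minute to be captured; the documents say only that treatment is recorded. The sensitivity run would have fewer values in the stopped sessions.
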